5.4 Withdrawal from trial and discontinuation of treatment

In accordance with legal requirements and International Council for Harmonisation (ICH) – Good Clinical Practice (GCP) guidelines, every subject has the right to refuse further participation in this trial (withdrawal from trial) or refuse further treatment (discontinuation of treatment) at any time and without providing reasons. A subject's refusal should be effectuated immediately upon his/her request.

In addition, a subject may be withdrawn from the trial or be discontinued from treatment at any time at the discretion of the investigator.

Reasons for withdrawal from trial or discontinuation of treatment include (but are not necessarily limited to) progressive disease, AE, pregnancy, death, protocol violation, and lost to follow-up. If the IMP application is discontinued regardless of the reason for discontinuation, the subject should be encouraged to continue in the trial.

The reasons for trial withdrawal or treatment discontinuation are to be fully documented on the electronic case report form (eCRF) and an EoT visit should be completed as soon as possible to the extent possible. Subjects who withdraw from trial before randomization will be considered screen failures. In case of treatment discontinuation, the subject should be encouraged to attend remaining trial visits in line with the schedule of assessments (SoA). If a subject is withdrawn from the trial due to an AE or treatment is discontinued due to an AE, the AE must be followed up as outlined in Section 7.12.2.

If subjects are diagnosed with or have symptoms suggestive of COVID-19 they may not be allowed to attend trial visits until local regulations allow it. Subjects who are diagnosed with COVID-19 after randomization may subsequently be asked to complete trial visits (to the extent possible) via phone until applicable negative test results can be provided (if necessary, additional trial supplies may be shipped to the subject) or be withdrawn from the trial at the discretion of the investigator.

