Diary (Handout)	Х	Х	Х		Х		Х			
Biopsy ¹⁵		Х							Х	
Tape stripping ¹⁶		Х							Х	
Prior & concomitant therapies ¹⁷	Х	Х	Х	Х	Х	Х	Х	Х	Х	Х
Adverse events		Х	Х	Х	Х	Х	Х	Х	Х	Х
Investigational medicinal product (IMP) dispensation		Х			Х		Х			
IMP return, compliance and accountability					Х		Х		Х	
IMP application ¹⁸				_	Х					
Diary (Review)		Х	Х		Х		Х		X	

- 1. Follow-up (FU) visit is only applicable if there are ongoing serious adverse events (SAEs) or related adverse events (AEs) at Week 12. (X) indicates assessments to be performed if judged necessary by the investigator.
- 2. An unscheduled visit can be conducted to perform any of the postbaseline assessments or procedures included in the SoA if deemed necessary by the Investigator.
- 3. In the case of trial withdrawal or treatment discontinuation, all assessments of the Week 12 (End of Treatment [EoT]) visit have to be performed. The end of treatment form must be completed when treatment is discontinued and the end of trial form must be completed at end of the trial or in case of trial withdrawal.
- 4. Phone calls: To remind subjects about diary documentation (in particular once-daily WI-NRS assessments that must be performed for 8 days leading up to each on-site visit [i.e., from day -7 to day 0 where day 0 = next on-site visit day]) and to ask for AEs. Phone visits may be replaced by in-clinic visits where relevant, e.g., in subjects going to the dialysis unit for haemodialysis.
- 5. Informed consent must be signed by both subject and investigator before any trial-related procedures are performed.

Clinical Trial Protocol

Protocol No. MC2-25-C1 Vers.3.0 EU/30-Nov-2022

- 6. At-home (diary) assessments must be performed for 8 days leading up to each visit, i.e., from day -7 to day 0 where day 0 = next on-site visit day.
- 7. The WI-NRS must also be reported by the subject at on-site visits
- 8. At all on-site visits, all patient-reported outcome (PRO) assessments should be completed before all other clinical assessments or procedures.
- 9. The trial staff must estimate the % body surface area treated based on the subject's indication of CKD-aP treatment area size on the CKD-aP treatment area diagram.
- 10. Physical exam: A complete physical examination is required at Screening and Week 12 (EoT or Early Termination) visits. An abbreviated physical examination is required at the Baseline visit (and if judged necessary by the investigator) at the FU visit if the FU visit is applicable.

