3.5 Safety Endpoints

- Frequencies of treatment-emergent adverse events (TEAEs), treatment-emergent serious AEs (TESAEs), treatment-related TEAEs (unlikely related, probably related, and possibly related), TEAEs leading to treatment discontinuation or trial withdrawal, and deaths during the trial for MC2-25 cream compared to MC2-25 vehicle.

- Mean change in vital signs (heart rate (HR), systolic blood pressure (SBP), diastolic blood pressure (DBP), and body temperature (temp)) from Baseline to Week 4, Week 8 and Week 12 for MC2-25 cream compared to MC2-25 vehicle.

Shift in frequencies of clinically significant and not clinically significant vital signs values from Baseline to Week 4, Week 8 and Week 12 for MC2-25 cream compared to MC-25 vehicle.

- Mean change in laboratory assessments (biochemistry and hematology) from Baseline to Week 4 and Week 12 for MC2-25 cream compared to MC2-25 vehicle. Shift in frequencies of normal, abnormal and abnormal clinically significant or not clinically significant laboratory values from Baseline to Week 4, Week 8 and Week 12 for MC2-25 cream

compared to MC-25 vehicle.

- Shifts in physical examination from Baseline to Week 12 by body area will be displayed. Frequencies of normal, abnormal and abnormal clinically significant and abnormal clinically not significant values of physical examination from Baseline to Week 12 for MC2-25 cream compared to MC-25 vehicle.
- Shifts in electrocardiograms (ECGs) from Baseline to Week 4 and Week 12 will be displayed. Frequencies of normal, abnormal and abnormal clinically significant and abnormal clinically not significant values from Baseline to Week 4 and Week 12 for MC2-25 cream compared to MC-25 vehicle.
- Percentage of subjects who missed 1 or more dialysis visits during the Double-blind Treatment Period as recorded on end of trial visit. Not applicable (NA) category will be presented for subjects not on dialysis.

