5.1 Methodological Considerations

General Conventions:

- SAS[®] software (version 9.4 or higher) will be used for all data analyses and tabulations.
- Data for all investigational centers will be pooled for analysis.
- Summary tables will report data based upon the protocol scheduled time points. For patients who are withdrew early from the study, all efficacy assessments captured at the EoT visit will be assigned to the nearest protocol scheduled time point.

Counts and percentages: Categorical variables will be described by summary tables of frequencies (counts and percentages) per treatment group

Descriptive Statistics:

Descriptive summaries of continuous data will include number of non-missing values, mean, standard deviation (SD), median, minimum, maximum and 1st Quartile (Q1) and 3rd Quartile (Q3). Descriptive summaries of categorical variables will include frequencies and percentages. Missing values will not contribute to the denominator of the percentages.

Statistical tests:

Hypothesis Testing- We assume the null hypothesis is that the MC2-25 cream performs less than or equal to the MC2-25 vehicle while comparing change from baseline in WI-NRS score to Week 12.

We assume for alternate hypothesis that there is significant difference between the treatments.

The hypothesis to be tested to address the objective is:

H0: Change from baseline in mean score of weekly mean of WI-NRS to Week 12 for MC2-25 cream (δ_0) <= Change from baseline in mean score of weekly mean of WI-NRS to Week 12 for MC2-25 vehicle (δ_1)

versus

H1: Change from baseline mean score of weekly mean of WI-NRS to Week 12 for MC2-25 cream (δ_0) > Change from baseline in mean score of weekly mean of WI-NRS to Week 12 for MC2-25 vehicle (δ_1)

The primary analysis will be conducted on Mean change in weekly mean WI-NRS Score recorded in the subject's diary from Baseline to Week 12 for MC2-25 cream compared to MC2-25 vehicle and will be analyzed by a mixed model of repeated measures (MMRM).

Statistical tests will be two-sided with $\alpha = 0.05$. Superiority is concluded if a p-value of statistical hypothesis testing is below the level and the estimate of treatment difference is in favorable direction for MC2-25 cream.

Due to the phase 2 type of the trial, no adjustment due to multiple testing will be used.

No interim analyses are planned. SAS[®] software will be used for all data analyses and tabulations.

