5.2.3 Analysis Windows

As subjects do not always adhere to the protocol visit schedule, the following rules are applied to assign actual visits to analysis visits. Listed below are the visit windows and the target days for each visit. The reference day is Baseline, Study day 1. If a subject has 2 or more actual visits in 1 visit window, the visit closest to the target day will be used as the protocol visit for that visit window. The other additional visit(s) will not be used in the summaries or analyses, but they can be used for determination of clinically important endpoints. If 2 actual visits are equidistant from the target day within a visit window, the later visit is used.

Table 10 represents the analysis windows assigned for efficacy and safety analysis and the corresponding range of treatment days (window) during which data for a particular nominal visit will be collected. The analysis windows will be calculated from the first application of study product. These are analysis windows that contain, but are not same as, the actual visit windows.

For assessments that are not planned on Week 1, the visit window for such assessments will be starting at Week 4.

Study Week/ Period	Study Visit	Target Day	Window
Screening	Visit 1 (V1)	-28 to -1	
Baseline/ Week 0 (on site)	Visit 2 (V2)	1	1
Week 1 (on site)	Visit 3 (V3)	8 (±1)	2-19
Week 4 (on site)	Visit 5 (V5)	29 (±4)	20-43
Week 8 (on site)	Visit 7 (V7)	57 (±4)	44-71
Week 12 (on site/EoT)	Visit 9 (V9)	85 (±4)	72-92
Week 14 (FU)	Visit 10 (V10)	±2 Weeks after EoT	

Table 10Study Period, Visit and Target Day

For the hypothetical strategy, subjects given prohibited therapies will have WI-NRS data set to missing for visits after the start of the prohibited therapies and then missing data will be estimated using MIs. Subjects with an ET visit will be excluded from the PPS analyses. Safety data collected during an ET visit will remain at the Week 12/EoT visit.

Note: As per the CDISC, baseline is defined as Day 1 and not as Day 0. Therefore, there is a difference of one day between study day as defined in protocol and target day (Table 10).

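### The Week 12 safety column mixes true Week 12 values with early-termination values from any study day, and the SAP does not say which record counts when a subject stops the cream but stays in the trial

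*SAP*

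**What the plan says.** SAP 5.2.3 states that Table 10 "represents the analysis windows assigned for efficacy and safety analysis". In that table Week 12 has target day 85 and window days 72-92. Where a subject has two or more visits in one window, "the visit closest to the target day will be used as the protocol visit for that visit window", and "The other additional visit(s) will not be used in the summaries or analyses", although an unused visit may still count towards clinically important endpoints.

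Later in the same section comes the rule at issue: "Safety data collected during an ET visit will remain at the Week 12/EoT visit". It has no day limit. Efficacy data from early withdrawals are handled differently under SAP 5.1: "all efficacy assessments captured at the EoT visit will be assigned to the nearest protocol scheduled time point". The SAP gives no reason for the difference.

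SAP 3.5 names fixed time points for the safety endpoints, for example "Mean change in laboratory assessments (biochemistry and hematology) from Baseline to Week 4 and Week 12". Vital signs are summarised at Weeks 4, 8 and 12, ECG shifts at Weeks 4 and 12, and physical-examination shifts at Week 12 only.

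The protocol allows one subject to have both a stopping visit and a later Week 12 visit. Table 3, footnote 3 says: "In the case of trial withdrawal or treatment discontinuation, all assessments of the Week 12 (End of Treatment [EoT]) visit have to be performed". Protocol 5.4 adds: "In case of treatment discontinuation, the subject should be encouraged to attend remaining trial visits".

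**The concern.** There are two difficulties.

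First, the ET rule overrides the day windows for safety data only. Laboratory values, vital signs, ECG and physical examination from a subject who left in the first weeks are summarised beside values from subjects with 12 weeks of follow-up, while efficacy scores from the same visit are filed by time. The column then estimates neither a clean Week 12 change nor, consistently, an end-of-treatment change.

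Second, a subject who stops the product but stays in the trial may have two candidate records, one at stopping and one off treatment at Week 12. The SAP does not say how to choose. If the closest-to-target rule is used, the record nearest the time of stopping is the one left out.

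Subjects who stop early include those who stop because of an adverse event, and the safety analysis is descriptive only (SAP 5.6), so these tables are the planned analysis of these parameters. Protocol 2.3 describes this as the first clinical trial of the cream.

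**Working it through.** **The plan's own figure.** Protocol 8.2 gives d = 1.5, s = 2.46, two-sided 5%, power of at least 80%, 2:1 allocation, 10% dropout and 108 randomised (72 cream, 36 vehicle).

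- Vehicle n = (1 + 1/2) × (1.960 + 0.842)² × (2.46/1.5)² = 1.5 × 7.849 × 2.690 = 31.7, so 32; cream 64; total 96.
- With 10% dropout: 96/0.90 = 106.7, so 107. The stated 108 is the next multiple of 3.

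The figure reproduces. Nothing below changes it; it supplies only the dropout rate and the arm sizes.

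**Where an ET safety record is filed.** Inputs are the Table 10 windows: Week 1, days 2-19; Week 4, days 20-43; Week 8, days 44-71; Week 12, days 72-92, target 85.

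| ET day | Table 10 window | ET sentence in SAP 5.2.3 | Days from target 85 |
|---|---|---|---|
| 4 | Week 1 | Week 12/EoT | 81 |
| 35 | Week 4 | Week 12/EoT | 50 |
| 65 | Week 8 | Week 12/EoT | 20 |
| 75 | Week 12 | Week 12/EoT | 10 |

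The two rules disagree for every ET visit on days 2-71. For assessments not planned at Week 1, the SAP starts the windows at Week 4.

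**How many subjects.** If every assumed dropout had an ET visit with safety data before Day 72:

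- 0.10 × 108 = 10.8, about 11 (0.10 × 72 = 7.2 cream; 0.10 × 36 = 3.6 vehicle).
- At 5%: 5.4 subjects. At 20%: 21.6 subjects.

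The documents give no ET-visit rate. The 5% and 20% figures are an assumed range.

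**How far the mean could move.** Let p be the share of Week 12 values that come from ET visits, and f the fraction of the full 12-week change that those values show. Reported/true change = (1 − p) + p × f.

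- p = 0.10, f = 0 to 0.5: 0.90 to 0.95.
- p = 0.05 to 0.20, same f: lowest 0.80 + 0.20 × 0 = 0.80; highest 0.95 + 0.05 × 0.5 = 0.975.

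The range for f is an assumption. If ET values were more abnormal than 12-week values (f above 1), the formula moves the other way, so the direction is not known.

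**Stopped the product, stayed in the trial.** A real Week 12 visit within the protocol's ±4 days falls on days 81-89, at most 4 days from target.

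- Stopping visit on Day 75: both records lie in the Week 12 window. The stopping record is 10 days from target, so the closest-to-target rule leaves it out.
- Stopping visit on Day 35, treated as an ET visit: it is held at Week 12/EoT, 50 days from target. If the duplicate rule is applied it loses, but that rule is written for visits in one window and Day 35 is not in days 72-92. The outcome is unspecified.
- Stopping visit on Day 35, with ET visit meaning trial withdrawal only: it falls in the Week 4 window, 6 days from target 29, and loses to a Week 4 visit held within ±4 days.

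The stopping value can therefore be left out on either reading of ET visit.

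**The case against.** The best defence is that the column is openly an end-of-treatment column. SAP 5.2.3 names the slot Week 12/EoT, Table 10 labels Visit 9 in the same way, and Protocol 7.4 to 7.8 schedule these assessments at Week 12 or early termination. On this view the ET sentence is a deliberate exception that follows the protocol. It also has a practical reason: physical examination has no planned visit between Baseline and Week 12, and laboratory tests and ECG have none at Week 8. Filing purely by day would leave an early physical examination, or an ECG or laboratory mean change from Days 44-71, without a planned summary row. Day-based filing would not stop displacement either, as the Day 35 example shows.

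Much of this stands. Simply deleting the ET sentence is not a good remedy, and a reader should not infer that early values are passed off as 12-week exposure, since the slot's name discloses the convention. It does not remove the problem, because SAP 3.5 defines the endpoints at Week 12 without that qualifier. Nor does the plan deliver a true end-of-treatment column for subjects who stop the product and later attend Week 12.

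A reader might also infer that the SAP requires the stopping record to be discarded. The documents do not go that far: ET visit is undefined, and the duplicate rule does not plainly reach a record from outside the window.

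Individual signals are also captured elsewhere. Values are listed by subject and visit (SAP 5.6.5), clinically significant abnormalities after screening are recorded as adverse events (Protocol 7.4 to 7.6 and 7.8), and adverse-event summaries do not use visit windows.

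**Conclusion.** The point holds as a defect in the descriptive safety summaries. SAP 5.2.3 places ET safety values from any day in the Week 12 column, against the stated scope of Table 10 and the endpoint definitions in SAP 3.5. It also leaves open which record is used for subjects who stop the product but stay in the trial.

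The size is modest. About 11 of 108 subjects is a ceiling under the 10% dropout assumption, not an expectation: dropouts may be lost to follow-up or die, and Protocol 5.4 asks for the EoT visit only as far as possible. It would be wrong to conclude that the column is uninformative, because at that dropout rate about 90% of subjects could still supply true Week 12 values. The 0.90 to 0.95 dilution rests on assumed values of f and illustrates scale only.

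No efficacy estimate, error rate or power figure changes, and listings and adverse-event reporting are unaffected. The correction is still worth making: it is cheap, needs no new data, and these tables are the planned summary of laboratory, vital-sign, ECG and examination findings.

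**What to change.** In SAP 5.2.3, replace the ET sentence with three statements:

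1. The Week 12 row of each safety table uses only visits on days 72-92.
2. A separate last on-treatment row, giving change and shift, is added for every safety parameter. It always includes the EoT or ET assessment made at stopping, even where no visit is planned in that window (physical examination before Day 72; ECG and laboratory values on Days 44-71). A later off-treatment visit never displaces it. Because the EoT visit may fall shortly after the last application, say that it still counts for this row.
3. ET visit is defined, stating whether it covers treatment discontinuation without trial withdrawal.

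Align the time-point labels in SAP 3.5 with these rows. A worst post-baseline row is optional and not needed to resolve the point.

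The cost is SAP wording, one extra row per safety table and a slightly smaller n at Week 12. No additional data are collected.

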5.2.4 COVID-19 Impacted Visits

Since the primary and secondary efficacy endpoints are derived from the subjects' diaries and summaries of other efficacy endpoints and safety endpoints are as observed, there will be no adjustments made for coronavirus disease of 2019 (COVID-19) impacted visits.

5.3 Demographics and Background Characteristics

Subject demographics and background characteristics will be summarized for the FAS, MFAS (if it differs from the FAS) and SAS using descriptive statistics by treatment group and overall. Demographics will include age, age-group (<=65, 66–79, and 80 and above years) sex, race,

ethnicity, weight, height, body mass index (BMI). BMI is derived using: BMI $(kg/m^2) =$ weight $(kg) / [height (m)]^2$. Background characteristics include CKD stage and duration, whether subjects are on dialysis or not and time in months (month will be calculated as number of days divided by 30) since initiation of dialysis. Number of times subject has dialysis in a week and use of anti-CKD-ap medication (see Section 6.3.2) at baseline will also be reported. Baseline weekly mean WI-NRS, time in months since start of CKD-aP, selected laboratory parameters (Serum Urea, Serum Creatinine) and, baseline CGA and CTA.

Medical and surgical history will be coded using the Medical Dictionary for Regulatory Activities (MedDRA) version 24.1 and will be summarized using descriptive statistics by system organ class (SOC), preferred term (PT) and by treatment group and overall. If a subject has more than one medical or surgical history event in an SOC or PT, the subject will be counted once within the term.

Subject demographics, background characteristics, and medical history will be listed by country, site and subject.

5.4 Subject Accountability

Subjects screened, reason for screen failure, subjects randomized, subject disposition, reason for withdrawal from trial, reason for discontinuation of treatment, and analysis populations will be summarized using descriptive statistics for the SS by treatment group and overall. Subjects screened, subject disposition and populations status will be summarized using descriptive statistics for the SS by site and by treatment group and overall. Major protocol deviations will be summarized using descriptive statistics using the SAS for all sites and by site and by treatment group and overall. Screen failures, subject disposition including reason for discontinuation, and protocol deviations will be listed by country, site and subject.

5.5 Efficacy Analyses

All efficacy summaries and analyses will be provided for the FAS, MFAS and PPS (if MFAS and PPS are different than FAS)

5.5.1 Primary Efficacy Analyses

The primary endpoint will be analyzed using a mixed model of repeated measures (MMRM) with baseline weekly mean WI-NRS as a covariate and treatment, CKD stage stratum at baseline, systemic CKP-aP treatment status at baseline and visit as fixed factors and subject as a random factor with a 2-sided $\alpha = 0.05$. An unstructured variance/covariance structure will be used. Least squares (LS) means and standard errors (SE) for each treatment group will be displayed along with the difference in LS means between active and vehicle with the corresponding SE, 95% confidence interval (CI) and p-value.

Descriptive summaries and listings by subject and visit will be provided.

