Secondary Endpoints:	• Percentage of subjects obtaining a \geq 4-point improvement in weekly mean
	WI-NRS recorded in the subject's diary from Baseline to Week 12 for
	MC2-25 cream compared to MC2-25 vehicle.
	• Percentage of subjects obtaining a \geq 3-point improvement in weekly mean
	WI-NRS recorded in the subject's diary from Baseline to Week 12 for
	MC2-25 cream compared to MC2-25 vehicle
	Wez zo eream compared to Wez zo vemere.
	• Percentage of subjects obtaining a complete response in weekly mean
	WI-NRS recorded in the subject's diary from Baseline to Week 12 for
	MC2-25 cream compared to MC2-25 vehicle. (Complete response is
	defined as scores equal to 0 or 1 in \geq 80% of the non-missing WI-NRS
	values recorded in the subject's diary 7 days prior to and including the
	visits.)
Other Endpoints:	Additional endpoints are included in the Clinical Trial Protocol.
Safaty Endnainta	 Frequencies of treatment-emergent adverse events (TEAEs) SAEs
Safety Endpoints.	adverse drug reactions (ADRs) AFs leading to treatment discontinuation
	or trial withdrawal and deaths during the trial for MC2-25 cream
	compared to MC2-25 vehicle
	compared to MC2-25 venicle.
	• Changes in mean safety assessments: vital signs (heart rate, systolic blood
	pressure, diastolic blood pressure, temperature), and blood samples
	(biochemistry, haematology) from Baseline to Week 12 for MC2-25 cream
	compared to MC2-25 vehicle.
	• Frequency of clinically significant abnormal physical examinations and
	ECGs from Baseline to Week 12 for MC2-25 cream compared to MC2-25
	vehicle.
	Percentage of subjects who missed 1 or more dialysis visits during the
	Double blind Treatment Period
	Double-office relation relation.
Statistical Methods:	Efficacy analysis: The primary endpoint of the trial, mean change in weekly
	mean WI-NRS recorded in the subject's diary from Baseline to Week 12 for
	MC2-25 cream compared to MC2-25 vehicle, will be analysed by a mixed
	model of repeated measures with Baseline weekly mean WI-NRS as covariate
	and treatment, CKD stage stratum at baseline, systemic CKD-aP treatment
	status at baseline and visit as fixed factors with a two-sided $\alpha = 0.05$.
	Treatment groups are compared for the superiority of MC2-25 cream over
	MC2-25 vehicle after 12 weeks of treatment. Due to the Phase II type of the
	trial, no alpha adjustment will be carried out for secondary endpoints.
	Satety Analysis: Satety data will be summarized using descriptive statistics (n,

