8.8.1 Primary endpoint

The primary endpoint, mean change in weekly mean WI-NRS recorded in the subject's diary from Baseline to Week 12 for MC2-25 cream compared to MC2-25 vehicle, will be analysed by a mixed model of repeated measures with Baseline weekly mean WI-NRS as covariate and treatment, CKD stage stratum at baseline, systemic CKP-aP treatment status at baseline and visit as fixed factors with a two-sided α =0.05. The weekly mean WI-NRS is calculated as the average of minimum 4 WI-NRS values recorded once daily in the subject's diary from 7 days prior to and including the visit days (i.e., must be recorded for 8 days total).

On the FAS, the primary analysis and one sensitivity analysis will follow a treatment policy strategy irrespective of any potential intercurrent events. On primary analysis, missing values will be replaced following a multiple imputation procedure adequate for the endpoint assuming missingness appearing at random and based on 20 imputations. On the FAS, sensitivity analyses will include imputation by last observation carried forward (LOCF; treatment policy strategy) and multiple imputation of missing data and all data after start of rescue medication (hypothetical strategy).

Applying the same statistical model, further estimands include multiple imputation on the MFAS and as observed on the PPS, both following a treatment policy strategy. If deaths occur, further estimands may be defined following a composite endpoint strategy.

Supportive subgroup analyses will be conducted by dialysis status and CKD stages and by country on the FAS.

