3.1 Primary Efficacy Endpoint

The primary efficacy endpoint is the mean change in weekly mean Worst Itch Numeric Rating Score (WI-NRS) recorded in the subject's diary from Baseline to Week 12 for MC2-25 cream compared to MC2-25 vehicle. Weekly mean WI-NRS is calculated as the average of all and at least 4 non-missing WI-NRS values recorded in the subjects' diaries for the 7 days prior to and including the scheduled in clinic visits (8 days in total expected). If less than 4 observations are recorded in the 8 days expected, the weekly mean WI-NRS will be considered missing.

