5.5.3 Other Efficacy Analyses

Descriptive summaries will be provided for all other efficacy endpoints by visit and treatment group. They will also be listed by subject and visit.

The mean change in weekly mean WI-NRS from baseline to Week 1, 4, and 8, respectively, will be analyzed like described for the primary efficacy analysis in Section 5.5.1.

The mean change in weekly mean WI-NRS will be assessed within treatment for both arms (MC2-25 cream and MC2-25 vehicle) for change from baseline for all visits i.e., Week 1, 4, 8 and 12 using a paired T-test.

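### The primary MMRM and the key secondary GEE have no treatment-by-visit term, so they estimate one effect pooled over Weeks 1, 4, 8 and 12 instead of the stated Week 12 effect

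*SAP*

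**What the plan says.** SAP 3.1 defines the primary endpoint as the change in weekly mean WI-NRS "recorded in the subject's diary from Baseline to Week 12 for MC2-25 cream compared to MC2-25 vehicle". The protocol synopsis compares cream with "MC2-25 vehicle after 12 weeks of treatment". The hypotheses in SAP 5.1 and the power statement in Protocol 8.2 are also for Week 12, and so is the key secondary endpoint in SAP 3.2 (improvement of at least 4 points).

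SAP 5.5.1 gives the model: "baseline weekly mean WI-NRS as a covariate and treatment, CKD stage stratum at baseline", then "systemic CKP-aP treatment status at baseline and visit as fixed factors and subject as a random factor". On covariance it states: "An unstructured variance/covariance structure will be used". The output is "Least squares (LS) means and standard errors (SE) for each treatment group will be displayed along with the difference in LS means", and no visit is named. Protocol 8.8.1 has the same main-effects list, ending "systemic CKP-aP treatment status at baseline and visit as fixed factors with a two-sided" alpha of 0.05.

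SAP 5.5.2 repeats the list for the GEE, with an exchangeable structure. SAP 5.5.3 says that the changes to Weeks 1, 4 and 8 "will be analyzed like described for the primary efficacy analysis in Section 5.5.1".

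Neither document gives a treatment-by-visit term, a Week 12 contrast, or a restriction of the model to Week 12 data.

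**The concern.** When treatment enters only as a main effect, the model holds the cream-vehicle difference constant across all visits in the fit. The reported LS-mean difference then averages the four post-baseline visits, with weights set by the estimated covariance matrix. The primary p-value would therefore not test the Week 12 hypothesis. An effect that builds up over 12 weeks is diluted. An early effect that fades can give a significant primary result with little or no difference at Week 12.

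The plan is also inconsistent with itself. The separate Week 1, 4 and 8 results requested in SAP 5.5.3 would all be the same number if taken from this model.

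There is a smaller wording fault. A random subject effect on top of an unstructured residual covariance is redundant and not identifiable, and a GEE has a cluster identifier but no random factor.

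**Working it through.** **1. The plan's own power figure (Protocol 8.2).** Inputs: d = 1.5, s = 2.46, two-sided 5%, allocation 2:1, 108 randomised (72 and 36), 10% dropout.

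- d/s = 1.5/2.46 = 0.61.
- Vehicle n for 80% power = (1.960 + 0.842)² × s² × (1 + 1/2) / d² = 7.85 × 6.05 × 1.5 / 2.25 = 31.7, so 32. The total is 96, and 96/0.9 = 107, against 108 stated.
- Power by noncentral t is 84.1% at 72 and 36. After dropout (72 × 0.9 = 64.8 and 36 × 0.9 = 32.4, taken as 65 and 32) it is 79.8%.

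The stated figure reproduces, for a comparison at Week 12.

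**2. What the written model estimates.** The diary visits after baseline are Weeks 1, 4, 8 and 12 (Protocol 7.9.1). Let δ be the vector of true effects at these visits and S the 4 × 4 covariance matrix. After imputation the data are complete, and generalised least squares with a single treatment effect gives:

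- estimate = w′δ, with w = S⁻¹1 / (1′S⁻¹1);
- variance = (1/n₁ + 1/n₂) / (1′S⁻¹1).

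**3. Numbers with equal SDs.** Assumed, because the documents do not give them: SD 2.46 at every visit, the between-visit correlation, and the effect profiles. Evaluable subjects are 65 and 32, so √(1/65 + 1/32) = 0.216.

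With autoregressive correlation 0.8 per four weeks, w = 0.415, 0.075, 0.085, 0.425 for Weeks 1, 4, 8 and 12. The pooled SD is 2.15, so SE = 2.15 × 0.216 = 0.465. The Week 12 contrast has SE = 2.46 × 0.216 = 0.531.

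- Gradual onset 0.3, 0.8, 1.2, 1.5: 0.415×0.3 + 0.075×0.8 + 0.085×1.2 + 0.425×1.5 = 0.92, which is 62% of the Week 12 effect.
- Fading 1.5, 1.5, 1.0, 0.5: 0.415×1.5 + 0.075×1.5 + 0.085×1.0 + 0.425×0.5 = 1.03, about twice the Week 12 effect.

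| True effect at Weeks 1/4/8/12 | Model targets | Power, model as written | Power, Week 12 contrast |
|---|---|---|---|
| 1.5/1.5/1.5/1.5 | 1.50 | 89% | 80% |
| 1.0/1.5/1.5/1.5 | 1.29 | 79% | 80% |
| 0.3/0.8/1.2/1.5 | 0.92 | 50% | 80% |
| 1.5/1.5/1.0/0.5 | 1.03 | 59% | 15% |
| 1.5/1.2/0.6/0 | 0.76 | 37% | 5% |

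Under compound symmetry 0.6 each visit has weight 0.25. The gradual profile then gives 0.95 with 56% power. For the last row, where Week 12 has no effect, rejection runs from 37% to 49% across compound symmetry 0.5 to 0.7 and autoregressive 0.7 to 0.8.

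**4. Unequal SDs.** If the SD of change grows with time, the early visits take most of the weight. With assumed SDs of 1.5, 2.0, 2.3 and 2.46, the gradual profile gives 0.34 (compound symmetry 0.6), 0.45 (autoregressive 0.7) or 0.28 (autoregressive 0.8). That is 19% to 30% of the Week 12 effect. This range moves with the assumed SDs and correlations.

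**5. The GEE.** One large simulated data set (30,000 subjects) was fitted with a logit link and exchangeable correlation. It assumed an effect building up linearly to Week 12 and autoregressive 0.7 data. Week 12 response was 41.7% versus 20.7%, an odds ratio of (0.417/0.583)/(0.207/0.793) = 2.74. The GEE without the interaction returned a single odds ratio of 2.26.

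**The case against.** The strongest reply is that the intention is clear. MMRM often implies a treatment-by-visit term, every statement of the endpoint says Week 12, SAP 5.5.3 wants results by visit, and SAP 5.5.1 names no visit for its LS-mean difference. On this reading the specification is incomplete, not wrong. That explains how the text may have arisen, but both documents list the fixed factors one by one without the interaction. A programmer who follows them will leave it out, and adding it later would be an unplanned choice on the primary test.

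Other points stand in part:

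- By-visit descriptive summaries are planned, so a fading effect would be visible. They supply no between-arm test at Week 12.
- The sizes depend on assumed profiles. With rapid onset (1.0, 1.5, 1.5, 1.5) the loss is small: a target of 1.29 with 79% power here, or 1.38 with 87% under compound symmetry 0.6. With a constant effect, pooling gains power. The plan argues for neither profile.
- A profile that is not constant could by chance average to the Week 12 value, so the mismatch holds in general, not in every case.
- The phase 2 objective is exploratory, but SAP 5.1 still concludes superiority from this p-value.
- A missing baseline-by-visit term and the random-factor wording are minor, and neither causes the pooling.

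**Conclusion.** The concern holds. As written, the primary MMRM and the key secondary GEE return one effect pooled over Weeks 1, 4, 8 and 12, while the endpoints, hypotheses and power are for Week 12. The algebra needs no assumption about the data; the size of the discrepancy does. With SD 2.46 at every visit, autoregressive correlation 0.8 and 65 versus 32 evaluable, a gradual effect is cut to 62% of its Week 12 value and power falls from 80% to 50%. In the other direction, an early effect that is gone by Week 12 is declared significant in 37% to 49% of trials across the equal-SD structures tried, against 5% for a Week 12 contrast. The sample size itself is correct for a Week 12 contrast. Because this decides what the primary p-value tests, it must be fixed before database lock.

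**What to change.** In SAP 5.5.1, add treatment-by-visit and, as good practice, baseline WI-NRS-by-visit to the MMRM. Define the primary result as the cream-minus-vehicle contrast at Week 12, with its SE, 95% CI and p-value. Take the Week 1, 4 and 8 contrasts for SAP 5.5.3 from the same fit. In SAP 5.5.2, add treatment-by-visit to the GEE and name the Week 12 contrast as the key secondary test. In both sections, replace the random-factor wording with subject as the repeated-measures or cluster identifier. Record the change from Protocol 8.8.1 and 8.8.2 in SAP 6.2.

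The cost is some SAP wording and a few lines of code. The statistical price is a wider interval if the effect really is constant over visits: in the example, SE 0.531 instead of 0.465, and power 80% instead of 89%.
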